 - g. Subject has a clinically significant abnormal 12-lead ECG that may jeopardize the subject's ability to complete the study or that may confound study results as determined by the Investigator, or a Screening centrally overread 12-lead ECG demonstrating any one of the following: heart rate > 100 beats per minute, heart rate < 50 beats per minute, QRS > 120 ms, QT interval corrected for heart rate using Fridericia's formula (QTcF) > 450 ms (males), QTcF > 470 ms (females), or PR > 220 ms. Subjects with an ECG that has a centrally overread overall interpretation of "abnormal, significant" or "abnormal, potentially clinically significant" must be discussed with the Medical Monitor.
 - h. Subjects with known history of human immunodeficiency virus (HIV) seropositivity.
 - i. Subject has type I diabetes mellitus or insulin-dependent type II diabetes.
11. Subject exhibits evidence of moderate or severe extrapyramidal symptoms, dystonia, tardive dyskinesia, or any other moderate or severe movement disorder. Severity to be determined by the Investigator.

12. Female subject who is pregnant or lactating.
13. Subject has a history of allergic reaction or suspected sensitivity to quetiapine or quetiapine XR or any substance that is contained in the quetiapine XR or SEP-363856 formulations.
14. Subject with a supine systolic blood pressure \geq 140 mmHg and/or supine diastolic blood pressure \geq 90 at Screening or Baseline. A repeat blood pressure measurement is allowed once during the Screening Period and once at Baseline. The repeat measurements can be used to determine eligibility. The repeat blood pressure measurement at Screening can be conducted on a different day within the screening period, if needed.
15. Subject has any clinically significant abnormal laboratory value(s) at Screening (hematology, chemistry and urinalysis) as determined by the Investigator. (Note: Retesting is allowed once during the Screening Period and the retest will be used to determine eligibility after approval from the Medical Monitor; however, the Screening Period will not be extended to accommodate repeat laboratory tests, unless repeat tests are needed due to a technical issue with laboratory sample processing, shipment or testing delay at the central laboratory. Abnormal findings of questionable significance will be discussed with the Medical Monitor prior to including any subject.)

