Version Number: 0.6

Version Date: 30JAN2023

Template No.: CS_TP_BS016 Revision 6

Reference: CS_WI_BS005

Effective Date: 02Dec2019

status is matching Baseline fasting status.

- By-visit summary of the number and percentage of subjects in each outcome category for qualitative measurements in urinalysis (as applicable) and for urine drug screening results. Urine drug screening results will be reported as “Positive”/ “Negative”.
- Shift in laboratory results (chemistry, hematology, urinalysis) from Baseline to Week 1/Visit 3, Week 4/Visit 5, Week 12/Visit 7, Week 24/Visit 10, Week 36/Visit 13, Week 52/Visit 17, and LOCF Endpoint according to the reference range criteria. The existing reference range indicators provided by the central laboratory will be mapped as needed to categories of “Normal” (within the reference range) / “Abnormal” (outside the reference range) for urinalysis non-pH results, and to categories of “Low” (below the reference range) / “Normal” (within the reference range) / “High” (above the reference range) for chemistry and hematology results as well as urinalysis pH results.
- Number and percentage of subjects with at least one potentially clinically significant (PCS) laboratory value (see [APPENDIX 8](#)) post-Baseline. The period of evaluation includes both the double-blind treatment period and the follow-up period up to and including 9 days after the last dose of study drug, including unscheduled visits. Subjects will be counted in a particular PCS category if they met that PCS criteria at least once during the period of evaluation, regardless of their Baseline value.

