17.3 ECG EVALUATIONS

Data from the centrally over-read ECG (Electrocardiogram) results will be included in the reporting of this study.

The following ECG parameters will be reported for this study:

- PR Interval (msec)
- RR Interval (msec)
- QRS Duration (msec)
- QRS Axis (deg)
- QT Interval (msec)
- QTcF Interval (msec) (Fridericia's Correction of QT interval)

Document: CCI

Author: PPD

Version Number: 0.6

Version Date: 30JAN2023

Template No.: CS_TP_BS016 Revision 6

Reference: CS_WI_BS005

Effective Date: 02Dec2019

- QTcB Interval (msec) (Bazett's Correction of QT interval)
- Heart Rate (bpm)
- Overall assessment of ECG as determined by the central over-read:
 - Normal
 - Abnormal, Insignificant
 - Abnormal, Potentially Significant
 - Abnormal, Significant
 - Not Evaluable
- ECG findings
 - ECG findings will only be listed. Other ECG data will be summarized in tables as well as presented in listings.
 - The following summaries will be provided:
- By-visit summary of observed values and change from Baseline values for quantitative measurements.
- By-visit summary of ECG overall assessment results as determined by the central over-read ("Normal", "Abnormal, Insignificant", "Abnormal, Potentially Significant", "Abnormal, Significant", "Not Evaluable").
- Shift in ECG overall assessment as determined by the central over-read from Baseline to Week 1/Visit 3, Week 4/Visit 5, Week 12/Visit 7, Week 24/Visit 10, Week 36/Visit 13, Week 52/Visit 17, and LOCF Endpoint.
- Number and percentage of subjects who met each of the QTc interval prolongation criteria (see [Section 17.3.1](#)). The period of evaluation includes both the double-blind treatment period and the follow-up period up to and including 9 days after the last dose of study drug, including unscheduled visits.
- Number and percentage of subjects with at least one PCS ECG value (see [Section 17.3.2](#)) post-

Document: **CCI**Author: **PPD**

Version Number: 0.6

Version Date: 30JAN2023

Template No.: CS_TP_BS016 Revision 6

Reference: CS_WI_BS005

Effective Date: 02Dec2019

Baseline. The period of evaluation includes both the double-blind treatment period and the follow-up period up to and including 9 days after the last dose of study drug, including unscheduled visits.

Subjects will be counted in a particular PCS category if they met that PCS criteria at least once during the period of evaluation, regardless of their Baseline value.

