17.3.1 QTc INTERVAL PROLONGATION CRITERIA

QTc interval prolongation will be identified in accordance with the following predefined criteria (same criteria apply to both QTcF and QTcB):

- >450 msec at any post-Baseline time point (including unscheduled visit) not present at Baseline
- >480 msec at any post-Baseline time point (including unscheduled visit) not present at Baseline
- >500 msec at any post-Baseline time point (including unscheduled visit) not present at Baseline
- ≥ 30 msec increase from Baseline for at least one post-Baseline measurement (including unscheduled visits) and < 60 msec increase from Baseline for all post-Baseline measurements (including unscheduled visits)
- ≥ 60 msec increase from Baseline for at least one post-Baseline measurement (including unscheduled visits)

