17.3.2 ECG POTENTIALLY CLINICALLY SIGNIFICANT CRITERIA

Potentially clinically significant ECG measurements will be identified in accordance with the following predefined PCS criteria:

Table 3: Predefined ECG PCS criteria.

ECG Parameter	PCS Low	PCS High
---------------	---------	----------

Document:	CCI		
Author:	PPD	Version Number:	0.6
Template No.: CS_TP_BS016 Revision 6		Version Date: 30JAN2023	
Effective Date: 02Dec2019			Reference: CS_WI_BS005

Heart Rate (beats/min)	--	≥100
PR Interval (msec)	--	≥210
QRS Interval (msec)	--	≥120

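### Lab and ECG PCS counts ignore Baseline status, so the tables cannot separate new abnormalities from those already present at entry; add a count restricted to subjects not meeting the criterion at Baseline

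*SAP*

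**What the plan says.** SAP 17.2 places a subject in a laboratory PCS category if they "met that PCS criteria at least once during the period of evaluation, regardless of their Baseline value". SAP 17.3 repeats the rule for ECGs: a subject counts on meeting the limit "at least once during the period of evaluation, regardless of their Baseline value". The limits are in Appendix 8 (labs) and Table 3 of 17.3.2 (ECG: heart rate from 100 bpm, PR from 210 ms, QRS from 120 ms). They are fixed values or multiples of the ULN, and none requires a change from Baseline.

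Two neighbouring analyses do take Baseline into account. Each absolute QTc threshold in 17.3.1 carries a Baseline condition, for example ">450 msec at any post-Baseline time point (including unscheduled visit) not present at Baseline". The vital-sign section (17.4) uses the same regardless-of-Baseline sentence, but its limits in Table 4 build in a change from Baseline.

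On eligibility, Protocol 8.2 (exclusion 10g) excludes on "a Screening centrally overread 12-lead ECG demonstrating any one of the following", the list including "heart rate > 100 beats per minute, heart rate < 50 beats per minute, QRS > 120 ms" and "QTcF > 470 ms (females), or PR > 220 ms". For laboratory parameters without a numeric limit, exclusion 15 relies on judgement: "Subject has any clinically significant abnormal laboratory value(s) at Screening (hematology, chemistry and urinalysis) as determined by the Investigator".

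**The concern.** A subject already beyond a PCS limit before the first dose becomes a post-Baseline PCS case simply by staying there, or by exceeding the limit once at any of six scheduled post-Baseline lab and ECG visits (Weeks 1, 4, 12, 24, 36 and 52) or at an unscheduled one. A subject whose value is improving can count in the same way.

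Long-term safety of SEP-363856 is the primary objective, and PCS tables are where a safety reader looks for outliers. If pre-existing cases are mixed in, the absolute rate on SEP-363856 looks higher than the rate of new findings, and the ratio between arms moves toward 1. No planned table shows PCS status at Baseline. Lab shift tables use reference ranges, so a High-to-High entry does not say whether a PCS limit was newly crossed. The ECG shift table uses only the overall over-read interpretation.

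**Working it through.** The plan gives no figure to reproduce. The check has two parts.

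**1. Can an eligible subject already meet a PCS limit?** PCS limits are from SAP Table 3 and Appendix 8; eligibility limits are from Protocol 8.2.

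| Parameter | PCS | Excluded at Screening | Overlap |
|---|---|---|---|
| PR | ≥210 ms | >220 ms | 210 to 220 ms |
| Heart rate | ≥100 bpm | >100 bpm | exactly 100 |
| QRS | ≥120 ms | >120 ms | exactly 120 |
| Total cholesterol, LDL, HDL, triglycerides | numeric limits | no numeric limit | possible, subject to investigator judgement |
| Prolactin | ≥5 × ULN | >200 ng/mL | if ULN ≤ 200/5 = 40 ng/mL |
| Creatinine | ≥177 µmol/L | ≥1.5 × ULN | only if ULN > 177/1.5 = 118 µmol/L |
| BUN | ≥10.7 mmol/L | ≥1.5 × ULN | only if ULN > 10.7/1.5 = 7.13 mmol/L |
| ALT, AST | ≥3 × ULN | ≥3 × ULN | none |
| Glucose | >13.9 mmol/L | ≥7.0 mmol/L (fasting) | none |
| HbA1c | ≥7.5% | >7.0% | none |

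The ULNs are not in the documents. For an assumed prolactin ULN of 15 to 30 ng/mL, the PCS limit is 75 to 150 ng/mL, inside the eligible range. The table compares Screening limits; the numeric ECG exclusions do not apply to the Visit 2 ECG.

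For PR, recurrence after Baseline is likely. A subject whose true PR is exactly 210 ms, with independent symmetric variation (assumed), has a 1 − 0.5^6 = 98.4% chance of at least one PCS value over six scheduled ECGs.

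**2. What does this do to the reported rates?** Let q be the share of each arm meeting the criterion at Baseline, all persisting, and e the new-onset rate among the rest. Then the counted rate is q + (1 − q)e, and the difference between arms is (1 − q)(e₂ − e₁). Neither q nor e is in the documents; all values below are assumed.

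With e = 2% vs 6% (true ratio 3.0, true difference 4.0 points):

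| q | Lower-rate arm | Higher-rate arm | Ratio | Difference |
|---|---|---|---|---|
| 1% | 0.01 + 0.99 × 0.02 = 2.98% | 0.01 + 0.99 × 0.06 = 6.94% | 2.3 | 3.96 |
| 2% | 0.02 + 0.98 × 0.02 = 3.96% | 0.02 + 0.98 × 0.06 = 7.88% | 2.0 | 3.92 |
| 10% | 0.10 + 0.90 × 0.02 = 11.8% | 0.10 + 0.90 × 0.06 = 15.4% | 1.3 | 3.60 |

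With e = 5% in both arms and q = 2%, 5% or 10%, the table would report 6.9%, 9.75% or 14.5%. Pre-existing cases would be q divided by the counted rate: 29%, 51% or 69% of those listed. In a planned arm of 200 on SEP-363856 (two thirds of 300), that is 4, 10 or 20 subjects.

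**The case against.** The strongest reply is that this is a disclosed, inclusive reporting convention. The SAP speaks of post-Baseline values and does not call them treatment-emergent. Protocol 15.3.6.2 likewise asks for subjects with a PCS laboratory value after Baseline and is silent on Baseline status. By-visit change summaries, reference-range shifts, lipid, glucose and HbA1c summaries by Baseline metabolic impairment, and PCS listings give some context. Counting everyone also keeps in view a subject who starts just over a limit and then worsens badly; replacing the count would drop that subject from the table. This stands, and it is why the present count should stay. It does not close the gap, because none of those outputs tabulates new crossings of a PCS limit.

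It is also fair that the overlap is uneven. Only PR has a range proved from the documents' own numeric limits. Lipids still pass through investigator judgement. The prolactin limit applies at Screening, before psychotropic washout is complete, and values above 100 ng/mL need discussion with the Medical Monitor. Screening eligibility therefore does not establish Baseline prevalence, still less persistence.

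A reader might infer that the metabolic and prolactin comparison, a stated safety objective, is itself weakened. The documents do not support that. The comparison is tested by rank ANCOVA on change from Baseline, adjusted for Baseline rank (SAP 17.2, and 17.4 for weight and BMI). No test is planned on PCS counts, so there is no power to lose. Nor does the concern reach the QTc or vital-sign criteria.

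**Conclusion.** The concern holds as a limitation of the descriptive lab and ECG PCS tables: they cannot distinguish a new abnormality from one carried in. The consequence is inflated rates and a ratio pulled toward 1. The size depends on Baseline prevalence, which is unknown: at 1% to 2% the assumed ratio of 3.0 falls to 2.3 or 2.0, and at 10% to 1.3, while the difference falls at most from 4.0 to 3.6 points. Those figures assume full and equal persistence in both arms; less persistence means a smaller effect.

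Two stronger conclusions would go too far. It is not a bias toward either drug, since randomization should balance pre-existing cases in expectation. It is also not a conflict between SAP and protocol. The point is a cheap improvement to interpretation, strongest for PR and for laboratory parameters with no numeric entry limit.

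**What to change.** Keep the all-subject PCS count in SAP 17.2 and 17.3. Beside it, add the number and percentage of subjects who meet each criterion after Baseline but did not meet it at Baseline, with subjects not meeting it at Baseline as the denominator. A table crossing Baseline PCS status with post-Baseline PCS status would serve equally well and keeps those who started over the limit visible. Either extends to labs, PR, heart rate and QRS the condition already used for the QTc thresholds.

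No new data are needed, since SAP 6.2 already derives Baseline for these parameters. The cost is one extra set of tables, a short programming condition, and slightly smaller denominators in the restricted count.

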Observed values and changes from Baseline in clinical laboratory tests (hematology, chemistry and urinalysis), vital sign parameters (temperature, body weight, BMI, waist circumference, blood pressure [supine and standing], heart rate [supine and standing], and respiratory rate) and 12-lead ECG parameters will be summarized descriptively by treatment group. The frequency and severity of suicidal ideation and suicidal behavior based on the C-SSRS will be provided.

[figure not shown]
A nonparametric rank analysis of covariance (ANCOVA) will be applied to Week 52 prolactin, HbA_{1c}, lipids, and glucose levels, as well as body weight and BMI in order to compare changes from Baseline values between treatment groups with adjustments for Baseline value.

Movement disorder abnormalities will be assessed using the SAS, BARS, and AIMS scales. Mean changes from Baseline in these measures by scheduled visit will be presented.

HCRU responses will be summarized descriptively.

Descriptive statistics will be presented on the change from Baseline in PANSS total and subscale scores, CGI-S score, BNSS total score, MADRS total score, ESS total score, BACS composite score, SLOF total and subscale scores, EQ-5D-5L scores, UPSA-B total score and MSQ score. The proportion of subjects who achieve a response, defined as a 20% or greater improvement in PANSS total score from Baseline will be calculated. Time to relapse and time to all cause discontinuation will be analyzed with Kaplan-Meier methods.

CCI

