15.3.6.2. Clinical Laboratory Assessments

Clinical laboratory parameters will be summarized by presenting shift tables and through by visit summaries of the observed values and the change from Baseline values by treatment. For parameters with categorical outcomes, the number and percentage of subjects with each outcome will be summarized by visit. The number and percentage of subjects with at least one potentially clinically significant (PCS) value post Baseline for selected parameters will also be presented. PCS criteria for clinical laboratory parameters will be provided in the SAP.

The change from Baseline values will be analyzed by nonparametric rank ANCOVA to compare between the SEP-363856 and quetiapine XR treatment groups for: lipid (total cholesterol, LDL cholesterol, HDL cholesterol, and triglycerides), glucose, HbA1c and prolactin levels. Details of the rank ANCOVA analysis will be provided in the SAP.

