2.1.2. OTHER SAFETY OBJECTIVES

The other safety objectives are:

- To evaluate the long-term safety and tolerability of SEP-363856 by assessing:
 - Physical examinations (PE)
 - 12-lead electrocardiograms (ECG)
 - Vital sign measurements

Document:

CCI

Author:

PPD

Version Number:

0.6

Version Date:

30JAN2023

Template No.: CS_TP_BS016 Revision 6

Reference: CS_WI_BS005

Effective Date: 02Dec2019

- Clinical laboratory tests
- Suicidality using the Columbia – Suicide Severity Rating Scale (C-SSRS)
- Movement disorder abnormalities using the modified Simpson-Angus Scale (SAS), the Barnes Akathisia Rating Scale (BARS) and the Abnormal Involuntary Movement Scale (AIMS)
- To evaluate the effects of SEP-363856 (50 to 100 mg/day) on prolactin, HbA1c, lipids, and glucose concentrations, body weight, and body mass index (BMI) compared to Quetiapine XR (400 to 800 mg/day)
- To evaluate the impact of SEP-363856 on healthcare resource utilization

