3.2. METHOD OF ASSIGNING SUBJECTS TO TREATMENT GROUPS

The randomization schedule is generated by a non-study biostatistician.

The randomization is stratified by country and the randomization schedule is based on permuted blocks.

Once a subject is deemed eligible to be randomized at Day 1, an interactive web response system (IWRS) will perform treatment assignment. Subjects will be randomized to one of the following treatment groups in a 2:1 ratio:

- Flexibly dosed SEP-363856 (50, 75, or 100 mg/day) for 52 weeks
- Flexibly dosed Quetiapine XR (400, 600, or 800 mg/day) for 52 weeks

Once a randomization number has been assigned, it cannot be reused.

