7.2. MULTICENTER STUDIES

This study will be conducted by multiple Investigators at multiple centers in the US and non-US countries, including Russia, Romania, and Ukraine. Randomization is stratified by country.

When specified, statistical analysis will be adjusted for country.

Document: CCI

Author: PPD

Version Number: 0.6

Version Date: 30JAN2023

Template No.: CS_TP_BS016 Revision 6

Reference: CS_WI_BS005

Effective Date: 02Dec2019

A term for treatment-by-country interaction at Week 52/Visit 17 will be explored as part of the subgroup analysis (see [Section 16.1.1.4](#)). A significant interaction effect is defined as having a nominal p- value ≤ 0.10 . Additionally, graphical methods (i.e. Forest plots) will be used to present the analysis results separately for each country and to assess whether the interaction, if there is one, is quantitative (i.e. the treatment effect is consistent in direction but not in size) or qualitative (i.e. the treatment is beneficial for some but not for other countries).

Center pooling will not be implemented in the analyses for this study.

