7.4. MULTIPLE COMPARISONS/ MULTIPLICITY

No multiplicity adjustment is defined for analysis. Nominal p-values (i.e. without multiplicity adjustment) will be reported for statistical tests.

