- The change from Baseline values at Week 52/Visit 17 and LOCF Endpoint for selected laboratory parameters will be evaluated using a nonparametric rank ANCOVA analysis to compare SEP-363856 50 to 100 mg/day and Quetiapine XR 400 to 800 mg/day treatment groups. Baseline values and change from Baseline values will be ranked. A linear regression analysis will be performed on the change from Baseline value ranks with the Baseline value ranks as the independent variable, to produce regression residuals. Using the values of the residuals as scores, the Cochran-Mantel-Haenszel row mean scores test will be used to compare between the SEP-363856 and Quetiapine XR treatment groups. This analysis will be conducted for prolactin (overall and by sex), glucose (overall and fasting), insulin (overall and fasting), HOMA-IR (overall and fasting), lipid panel (overall and fasting), and HbA1c.

In order to assess the potential cardiometabolic effect of SEP-363856, select laboratory parameters will be summarized based on the subgroup of subjects who are identified to be metabolically impaired at Baseline (see [Section 17.2.3](#)) and on the subgroup of subjects who are non- metabolically impaired at Baseline. The following summaries will be provided on this subset of subjects:

Document: **CCI**

Author: **PPD**

Version Number: 0.6

Version Date: 30JAN2023

Template No.: CS_TP_BS016 Revision 6

Reference: CS_WI_BS005

Effective Date: 02Dec2019

- By-visit summary of observed values and change from Baseline values for LDL, HDL, total cholesterol, triglycerides, glucose, and HbA1c. LDL, HDL, total cholesterol, triglycerides, and glucose results will be summarized by fasting status: fasting only and overall (fasting, non-fasting, or fasting status unknown combined). Change from Baseline for LDL, HDL, triglycerides, and glucose results will only be calculated if post-Baseline fasting status is matching Baseline fasting status.

All laboratory data will be provided in data listings, with the values outside the reference ranges flagged. In addition, separate listings will be provided to present the laboratory data that met the PCS criteria.

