17.4 VITAL SIGNS

The following Vital Signs measurements will be reported for this study:

- Supine and Standing SBP (mmHg)
- Supine and Standing DBP (mmHg)
- Supine and Standing Pulse Rate (bpm)
- Respiratory Rate (breaths/min)
- Temperature (°C)
- Weight (kg)
- BMI (kg/m²)
- Waist Circumference (cm)

The following summaries will be provided for vital signs data:

- By-visit summary of observed values and change from Baseline values for vital sign measurements, including Follow-up/Visit 18.
- Number and percentage of subjects with at least one PCS vital sign value (see [Section 17.4.2](#)) post-Baseline. The period of evaluation includes both the double-blind treatment period and the follow-up period up to and including 9 days after the last dose of study drug, including unscheduled visits. Subjects will be counted in a particular PCS category if they met that PCS criteria at least once during the period of evaluation, regardless of their Baseline value.
- Number and percentage of subjects with orthostatic hypotension and/or orthostatic tachycardia (see

Document: **CCI**

Author: **PPD**

Version Number: 0.6

Version Date: 30JAN2023

Template No.: CS_TP_BS016 Revision 6

Reference: CS_WI_BS005

Effective Date: 02Dec2019

Section 17.4.1). The data will be summarized for Baseline and the overall post-Baseline period (which covers both the double-blind treatment period and the follow-up period up to and including 9 days after the last dose of study drug, including unscheduled visits), as well as by visit, including Follow-up/Visit 18.

- By-visit summary of BMI category and shift in BMI category from Baseline to each post-Baseline time point. BMI categories are listed in Section 7.5.
- By-visit summary of observed values and change from Baseline values for vital signs measurements by BMI category.
- The change from Baseline values at Week 52/Visit 17 and LOCF Endpoint for weight and BMI will be analyzed using nonparametric rank ANCOVA similarly to the analysis described in Section 17.2.
- By-visit summary and PCS summary based on metabolically impaired subjects at baseline (see Section 17.2.3) and non-metabolically impaired subjects at baseline.

All vital signs data will be provided in a data listing. In addition, a separate listing will be generated to present the vital signs data that met the PCS criteria. All occurrences of orthostatic hypotension and orthostatic tachycardia will also be presented in a listing.

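### The rank ANCOVA serving the safety objective worded as a comparison with quetiapine XR names no country stratum and no adjusted between-arm difference: a cheap efficiency gain, not a validity problem

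*SAP*

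**What the plan says.** One of the other safety objectives (SAP 2.1.2) is to evaluate SEP-363856 on prolactin, HbA1c, lipids, glucose, "body weight, and body mass index (BMI) compared to Quetiapine XR (400 to 800 mg/day"). Among the visible objectives, it is the only one worded as a comparison with quetiapine.

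The Protocol synopsis says a rank ANCOVA will "compare changes from Baseline values between treatment groups with adjustments for Baseline value". Protocol 15.3.6.2 then passes the detail on: "Details of the rank ANCOVA analysis will be provided in the SAP".

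SAP 17.2 supplies it. Baseline and change are ranked, change ranks are regressed on Baseline ranks alone, and "Using the values of the residuals as scores, the Cochran-Mantel-Haenszel row mean scores test will be used to compare" the arms, at Week 52 and at LOCF. SAP 17.4 carries the method over: weight and BMI "will be analyzed using nonparametric rank ANCOVA similarly to the analysis described in" Section 17.2.

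On design, SAP 3.2 states: "The randomization is stratified by country and the randomization schedule is based on permuted blocks". On adjustment, SAP 7.2 states: "When specified, statistical analysis will be adjusted for country". Sections 17.2 and 17.4 do not specify it. On inference, SAP 7.4 states: "Nominal p-values (i.e. without multiplicity adjustment) will be reported for statistical tests".

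**The concern.** Two things are missing from the visible description.

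- **The stratum.** The randomisation factor is absent from the test. Elsewhere the SAP uses it: the parametric ANCOVA in 16.1.1.3 has country as a factor, and the movement scales in 17.6, whose objective has no comparator wording, inherit that model.
- **The estimate.** A CMH row mean scores test on residuals gives a p-value. The 95% default in SAP 6.6 creates no interval here, because no estimate is named. The same movement scales do get an LS mean difference with a 95% CI.

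At stake is efficiency in a safety comparison. A conservative test is more likely to miss a real metabolic difference. Without an adjusted contrast and its precision, a non-significant nominal p-value does not separate no difference from too little information.

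**Working it through.** The documents give no power figure to reproduce: SAP 3.4 rests the sample size on clinical considerations.

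**Inputs from the documents.** 300 randomised 2:1, so 200 and 100. About 80 one-year completers on SEP-363856, so 80/200 = 40%. Two-sided 5% (SAP 6.6). Four countries (SAP 7.1).

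**Assumed, not in the documents.** Country share of residual variance R2 = 0, 5, 10, 20%; country sizes 150/60/50/40; permuted blocks of 6; effect set for 80% normal-theory stratified power; retention at random and equal in both arms; half the subjects in each by-sex prolactin test.

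**Type I error, unstratified test.** Balance within country removes the country component from the true variance of the contrast, but the one-stratum variance still includes it. So alpha = 2 x [1 - Phi(1.96 / sqrt(1 - R2))].

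- All 300, R2 = 0, 5, 10, 20%: 0.050, 0.044, 0.039, 0.028. Simulated: 0.051, 0.046, 0.038, 0.029.
- 40% retained at random, with R2 replaced by 0.4 x R2: 0.050, 0.048, 0.045, 0.041. Simulated: 0.047, 0.047, 0.045, 0.041.
- Stratified test, simulated: 0.046 to 0.052.

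**Power by formula, all 300.** For 80% stratified power the standardised effect is 1.960 + 0.842 = 2.802. Unstratified power = Phi(2.802 - 1.96 / sqrt(1 - R2)).

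- 5%: Phi(2.802 - 2.011) = 78.5%, a gain of 1.5 points from stratifying.
- 10%: Phi(2.802 - 2.066) = 76.9%, a gain of 3.1.
- 20%: Phi(2.802 - 2.191) = 72.9%, a gain of 7.1.

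**Power by simulation.** This uses the rank test itself, pooled ranks and regression kept, 20,000 runs per cell, Monte Carlo SE about 0.3 points. Cells show unstratified/country-stratified power in %, with the change (taken before rounding) in brackets.

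| Setting | 0% | 5% | 10% | 20% |
|---|---|---|---|---|
| All 300 | 77.1/77.0 (0.0) | 74.9/76.4 (+1.5) | 73.5/76.7 (+3.2) | 69.0/76.1 (+7.1) |
| 40% retained | 75.1/74.5 (-0.7) | 74.4/75.5 (+1.0) | 71.1/74.3 (+3.2) | 66.3/74.3 (+8.0) |
| By-sex, all | 76.2/75.9 (-0.3) | 74.2/75.5 (+1.3) | 72.0/75.3 (+3.3) | 66.9/74.6 (+7.7) |
| By-sex, 40% retained | 73.5/71.4 (-2.1) | 71.4/71.5 (+0.1) | 69.2/71.4 (+2.1) | 64.0/70.5 (+6.4) |

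With region as the stratum, the last row becomes -0.7, +0.3, +1.0, +3.0.

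**Sensitivity.** A second simulation used country shares 40/30/15/15%, blocks of 3, ranking and regression within country, and 4,000 runs. At 300 subjects the changes were about -1, +0.7, +2.4, +7.3. At 120 subjects they were about -2, -1, +2, +8. The pattern is the same, but ranking within country costs more in small samples, which favours keeping the pooled ranks.

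**Precision of the missing contrast**, before any gain from adjustment: half-width 1.96 x sqrt(1/200 + 1/100) = 0.24 SD. With 80 and 40 analysed it is 1.96 x sqrt(1/80 + 1/40) = 0.38 SD.

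**The case against.** The plan follows its own rules. The Protocol asks for Baseline adjustment and gets it, and SAP 7.2 uses country only where a section says so. Other tests are also unstratified (EQ-5D chi-squared in 16.2.7, C-SSRS Fisher's exact in 17.6.1), and some models use region instead (16.1.6, 17.1.11). This stands: the point is an omission, and a reader who infers a contradiction would be wrong. The rule confirms that the less efficient test will be run; it does not remove the gain.

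A reader might infer false-positive inflation. The calculations show the opposite direction.

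A reader might also infer that the size of the difference cannot be seen. It can: SAP 17.2 and 17.4 tabulate change by arm, Appendix 1 sets mean and SD among the summary statistics, and boxplots of change are planned for most of these measures. Only an adjusted contrast and its precision are missing.

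The log-rank tests in SAP 9 and 16.2.12 name no stratum either, but Protocol 15.3.1 and 15.3.5 label those analyses exploratory, so the point does not extend to them.

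The gain rests on a country variance share that no document gives, and change adjusted for Baseline already removes part of any stable country difference in level. This stands. Un-normalised local laboratory results from the Russia-Ukraine regions (SAP 17.2) are a possible source of country variation, but their effect is unknown and stratifying does not normalise them.

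Finally, Appendix 3 is blacked out and the output templates are not public, so either could already name a stratum or an estimate.

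**Conclusion.** The point holds as a minor, low-cost improvement. In the visible text, the rank ANCOVA behind the one comparatively worded safety objective omits the randomisation stratum and gives no Baseline-adjusted difference or CI.

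Stratifying gains little at a country share of 5% or less, about 3 points at 10% and about 7 at 20% with all 300 analysed. If country is irrelevant, it costs at most 0.7 points in the full-sample tests and 2.1 in the by-sex Week 52 prolactin test.

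Two assumptions limit this. The variance shares are hypothetical. The conservative direction also relies on arms staying balanced within country, which uneven dropout by country and arm could disturb at Week 52. The 40% retention is approximate too, because SAP 6.4 maps later early-termination values to Week 52. Nothing here touches the primary AE endpoint, and every p-value concerned is nominal.

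**What to change.** 1. In SAP 17.2 and 17.4, keep the pooled ranks and the regression, and add country as the stratum of the CMH row mean scores test. Fix a rule before unblinding for pooling sparse non-US countries. The minimum of 2 subjects per arm in SAP 16.1.1.4 is one available threshold. For the by-sex prolactin tests use US/Non-US region, which limits the possible loss to 0.7 points but recovers only about half the gain.
2. At Week 52 and LOCF, add the difference with 95% CI from the ANCOVA already defined in SAP 16.1.1.3 (treatment, country, Baseline), on the log scale for skewed analytes if needed. Label it supplementary, because it may not agree with the rank-test p-value.

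The cost is SAP wording, one stratification variable and a difference-and-CI column. Counting by-sex and fasting versions, Section 17.2 has 3 (prolactin) + 2 (glucose) + 2 (insulin) + 2 (HOMA-IR) + 8 (four lipids, twice) + 1 (HbA1c) = 18 analyses. Weight and BMI make 20, each at two time points. No new data are needed. If the unpublished templates already contain these items, stating them in 17.2 and 17.4 is enough.
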